Based on preliminary data, it is expected that approximately 560 nulliparous births with at least a 2nd degree laceration will be observed at the Wexner Medical Center from our generalist clinic in one year providing nearly 50 potentially eligible births to screen each month. Recruitment is expected to last 4-6 months. Consistent with our goals to evaluate preliminary efficacy and the feasibility of recruiting, retaining and monitoring of patient adherence to therapy our study sample size is based on more lenient criteria than would be expected in a definitive randomized trial. Very preliminary evidence for the primary endpoint, VuAS suggests that the average scores in those untreated would be on average 0.8 (sd=0.8) (Eaton et al). We reasonably expect to be able to recruit and fund the treatment for up to **70 participants**, **randomized**, 1:1. Assuming 20% attrition of those initially randomized at the 6 week follow-up, 35 patients will complete their 6-week follow-up visit. We would have 80% power to reject the null hypothesis of equal means with 10% two-sided type I error for a 50% reduction in the VuAS score. This larger type I and II error rates are reasonable for a pilot efficacy evaluation.

Analysis plan

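### The stated 80% power does not follow from the plan's own inputs: 20% attrition from 70 leaves 28 per arm, not 35, and power is about 58%

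*Combined protocol and SAP*

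**What the plan says.** Under Statistical Methods, Sample size determination and recruitment, the plan gives these inputs:

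- Untreated VuAS mean and SD: "the average scores in those untreated would be on average 0.8 (sd=0.8", described as very preliminary evidence.
- Number randomised: "up to 70 participants, randomized, 1:1".
- Attrition and completers: "Assuming 20% attrition of those initially randomized at the 6 week follow-up, 35 patients will complete their 6-week follow-up visit".
- Power for a halving of the VuAS: "We would have 80% power to reject the null hypothesis of equal means with 10% two-sided type I error for a 50% reduction".

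The paragraph adds that error rates of this size are reasonable for a pilot efficacy evaluation. The Analysis plan sets the primary efficacy analysis as a comparison of week-6 VuAS between the groups by linear regression, adjusted for laceration degree. The plan states no SD for the treated arm and claims no gain in precision from the adjustment.

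**The concern.** The completer count conflicts with the sentence it stands in. Exactly 35 are allocated to each arm when 70 are split 1:1, so a figure of 35 after a 20% loss suggests that the loss was not applied. Read as a total, 35 completers would mean 50% attrition.

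The power claim also looked too high for a standardised effect of 0.5 in a sample this small. This paragraph is the plan's only quantitative support for the sample size. If true power is well below 80%, the chance of missing a real halving of symptoms is well above the 20% that the plan calls reasonable. The plan sets no rule for going on to a definitive trial. Even so, a null week-6 result reported beside an 80% power statement could be taken as stronger evidence against benefit than the trial can supply.

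**Working it through.** **Inputs, all from the sample size paragraph.** Untreated mean 0.8; SD 0.8; 50% reduction, so δ = 0.8 × 0.5 = 0.4; two-sided α = 0.10; 70 randomised 1:1; 20% attrition. One assumption is added: the SD of 0.8 applies to both arms, because only the untreated SD is given. The standardised effect is then 0.4 / 0.8 = 0.5.

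**Completers.** 70 × (1 − 0.20) = 56, and 56 / 2 = 28 per arm. The plan's 35 equals 70 / 2.

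**Attempt to reproduce 80%.** Normal approximation: power = Φ(δ / (SD × √(2/n)) − z), with n per arm and z = 1.645 for two-sided 10%.

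- n = 35: 0.4 / (0.8 × √(2/35)) = 2.092, and Φ(2.092 − 1.645) = Φ(0.447) = 67.2%.
- n = 28: 0.4 / (0.8 × √(2/28)) = 1.871, and Φ(1.871 − 1.645) = Φ(0.226) = 58.9%.

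The noncentral t distribution gives slightly lower values:

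| Completers | Two-sided 10% | One-sided 10% |
|---|---|---|
| 35 in total (17.5 per arm) | 42.3% | 57.1% |
| 28 per arm (20% attrition applied) | 58% | 71.7% |
| 35 per arm (no attrition) | 66.5% | 78.7% |

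No two-sided entry reaches 80%. With a common SD of 0.8, only the one-sided test at 35 per arm comes close (78.7%; 79.1% by the normal approximation).

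**What 80% would need.** n = 2 × (SD × (1.645 + 0.842) / δ)² = 2 × (0.8 × 2.487 / 0.4)² = 49.5, so 50 per arm. By the t distribution, 50 per arm gives 79.9% and 51 gives 80.6%. At 20% attrition that means 100 / 0.8 = 125 to 102 / 0.8 = 127.5, or about 125 to 128 randomised.

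**What 28 per arm can detect.** At two-sided 10%, 80% power holds for a difference of 0.54 by the t distribution (0.53 by the normal approximation). That is 0.54 / 0.8 = 67% of the control mean. For a difference of 0.4, the common SD would have to be 0.59 or less.

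**Sensitivity to the treated-arm SD (assumed values, two-sided 10%).**

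| Treated SD | 28 per arm | 35 per arm |
|---|---|---|
| 0.8 | 58% | 66.5% |
| 0.57 (variance proportional to the mean) | 69% | 77% |
| 0.4 (halves with the mean) | 75% | 83% |

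To reach 80% at 28 per arm, the treated SD would have to fall to about 0.23 to 0.26, depending on how the degrees of freedom are taken.

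**The case against.** The best counter-argument concerns variance. The plan never says the SD is the same in both arms, and VuAS items have a floor at 0, so a smaller spread around a mean of 0.4 is plausible. With a treated SD near 0.5 and 35 completers per arm, the two-sided test does reach 80%. The one-sided route is therefore not the only possible origin of the figure. That much stands: 58% is conditional on a common SD, and how the slip arose is inference. It does not rescue the claim, because the route needs an SD the plan does not state and also ignores the plan's own attrition. At 28 per arm, a treated SD of 0.4 still leaves power at about 75%.

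The slip could also lie elsewhere. If 35 per arm was the intended number of completers, then 70 / 0.8 = 87.5, so 88 would have to be randomised, not 70. The documents do not settle this.

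Other mitigations are weaker. Phone completion of questionnaires after a missed visit may reduce loss, but zero attrition gives only 66.5%. Adjustment for laceration degree would have to explain about 43% to 45% of the outcome variance to bring 28 per arm to 80%.

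Finally, this is a pilot whose size is set by what the team can recruit and fund. That is a fair reason to choose lenient error rates and to keep 70. It does not make the stated power correct.

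**Conclusion.** The concern holds. The completer figure is wrong on either reading and should be 56 in total, 28 per arm; this needs no statistical assumption. The stated 80% power is not delivered. On the plan's inputs with a common SD of 0.8 it is about 58% two-sided, so the type II error is about 42%, roughly double the 20% stated. Allowing the treated-arm SD to fall as low as 0.4 widens the range to about 58% to 75%, all below 80%. The attrition slip explains only part of the gap, since 35 per arm also falls short under a common SD of 0.8. The sample size paragraph must be corrected. The design and the number randomised need not change.

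**What to change.** Keep 70 and replace the completer and power sentences with text such as:

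> With 20% attrition, 56 participants (28 per arm) are expected to complete the 6-week visit. With an SD of 0.8 in both arms and a two-sided 10% test, power is about 58% for a difference of 0.4 (50% reduction); 80% power is reached for a difference of about 0.54 (67% reduction).

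If a one-sided 10% test was intended, the plan should say so and give power as about 72% at 28 per arm. If a smaller treated-arm SD was assumed, it should be stated and justified. Presenting the primary result as an estimate with a 90% confidence interval would suit the pilot aim, but the correction does not depend on it.

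The cost is one reworded paragraph and a less favourable power statement, with no extra participants.

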Specific Aim 1: To evaluate the feasibility (recruitment, retention and adherence to therapy) and preliminary efficacy of local estrogen on vulvovaginal atrophy in the postpartum period.

Hypothesis: Use of low-dose vaginal estrogen in the postpartum period will decrease postpartum vaginal atrophy and associated symptoms.

We chose a validated measurement of vulvovaginal symptoms as our primary measure of vulvar atrophy. The Vaginal Vulvar Assessment Scale tools will be utilized during an exam at 6 weeks and 12 weeks. The tool also has a scale for physical exam findings associated with atrophy that will be recorded as well. Given most postpartum visits are scheduled at four to six weeks following a vaginal delivery for an uncomplicated

pregnancy and acute surgical wounds usually complete healing within two to four weeks, six weeks was deemed appropriate timing for vulvar assessment. The primary outcome for the study is Vulvar Assessment Scale (VuAS) at 6 weeks. Vaginal pH and maturation index will be obtained at follow up postpartum visits to further assess atrophy. Vaginal pH will be obtained in a standardized manner by swabbing indicator strips with pH range of 4.0 to 7.5 against the distal posterior vagina and interpreted by the examiner. Vaginal maturation will also be obtained via vaginal smears at the introitus and sent for quantitative assessment. Presence of granulation tissue and visible healing abnormalities such as suture line disruption, visible sutures, abscess, hematoma, and need for reoperation will be noted.

Specific Aim 2: To estimate the effect of local vaginal estrogen in the postpartum period on perineal pain, quality of life, and sexual function.

Hypothesis: Use of low-dose vaginal estrogen in the postpartum period will improve vaginal and perineal pain, quality of life measures and sexual function.

These will be assessed using validated questionnaires consisting of a visual analog scale for pain (VAS), Edinburgh Postnatal Depression Scale (EPDS), the Urinary Distress Inventory-6 (UDI-6), the Fecal Incontinence Severity Index for bowel symptoms (FISI), and the Female Sexual Function Index (FSFI). These questionnaires will be completed on day of randomization and postpart um visits at 6 weeks and 12 weeks.

Specific Aim 3: To compare patient satisfaction, ease of product use, likelihood of continued use, and rates of adverse events for the vaginal estrogen and placebo groups.

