Demographic and baseline characteristics of all participants will be summarized and presented overall and by assigned treatment group. We would expect approximate balance of observed and unobserved participant characteristics between study groups. Any chance imbalance in characteristics known to be related to primary or secondary outcomes will be considered as adjustment variables in outcomes analyses. Analysis of the primary outcome, VuAS at 6 weeks, will be compared regardless of treatment adherence or dose of intervention received (intent to treat analysis, (ITT). Primary efficacy analysis comparing VuAS scores at 6 weeks between the randomized groups will be estimated via linear regression, adjusting for stratification factor of laceration degree. Further analysis will consider adjustment for chance imbalances in key patient characteristics. Secondary analyses will investigate the VuAS at later time points, through linear mixed models or linear generalized estimating equation models (GEE), accounting for correlation over time. Recruitment screening counts, refusal rates, and retention rates will be reported overall and by treatment group. All statistical analysis will be performed using SAS or STATA. Data will be presented according to CONSORT 2010 guidelines for randomized controlled trials.

Data capture

All study data will be collected using standardized electronic case report forms (CRF)s in REDCap. The study team (Pls and study statisticians) will develop CRFs for data capture for both patient reported and data abstracted from the medical record. [name] and [name] will monitor all incoming data, with particular attention to: 1) enrollment and follow-up reports as entered into the database, 2) potential adverse events, and 3) missing data (for complete visits and for particular items) or extreme values. Regular reporting to the study team will work to reconcile or report issues as needed and to monitor participant retention.

Pitfalls and Solutions

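### The primary week-6 VuAS regression pre-specifies no pre-treatment symptom covariate, although the text says a 0–100 perineal pain score is collected at baseline: a modest precision point, not a bias

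*Combined protocol and SAP*

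**What the plan says.** **Primary model.** Under Statistical Methods, Analysis plan, the comparison of VuAS at 6 weeks "will be estimated via linear regression, adjusting for stratification factor of laceration degree". That factor has two levels, 2nd degree versus 3rd/4th degree (Randomization section). The same paragraph says that adjustment for chance imbalances in patient characteristics will be considered. It names no variable and no threshold.

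**Timing of VuAS.** Specific Aim 1 states: "The Vaginal Vulvar Assessment Scale tools will be utilized during an exam at 6 weeks and 12 weeks". The Approaches section and section F give the same two visits. No pre-treatment VuAS is described.

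**Timing of the pain score.** Specific Aim 2 lists a visual analog scale for pain among its questionnaires and adds: "These questionnaires will be completed on day of randomization". The later Aim 2 text (Background and Research Design) again describes a baseline administration and gives the pain scale a range of 0 to 100.

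**Visit table.** In the text available here the columns are displaced. Each Aim 2 questionnaire shows two marks, and no row is clearly the perineal pain scale. A VAS row sits among the Aim 1 items, but the protocol uses VAS both for the Vaginal Assessment Scale and for the pain scale. The table therefore neither confirms nor refutes a baseline pain score.

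**The concern.** A linear model for a symptom score usually gains precision from a pre-treatment measure of the same or a related symptom. The primary outcome has no such measure of its own. VuAS rates dryness, soreness, irritation and pain, so among the questionnaires described as completed at baseline, the perineal pain score is close in content. It is given no pre-specified role in the primary model.

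The imbalance clause does not fill the gap. A prognostic covariate reduces residual variance even when the arms are balanced on it, so waiting for an imbalance gives up that gain. Choosing covariates after the data are seen also leaves discretion that a pre-specified model would remove. At stake is some precision in a trial whose size is capped by funding: the plan expects to "recruit and fund the treatment for up to 70 participants".

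**Working it through.** **Inputs from Sample size determination and recruitment.**
- Control mean and SD: "the average scores in those untreated would be on average 0.8 (sd=0.8".
- Effect: "for a 50% reduction in the VuAS score", so 0.8 × 0.5 = 0.4 points, or 0.4/0.8 = 0.5 SD.
- Error rates: "We would have 80% power to reject the null hypothesis of equal means with 10% two-sided type I error".
- Completers: 70 randomised 1:1 with 20% attrition gives 70 × 0.8 = 56, or 28 per arm.

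**Step 1: the plan's own figure.** Completers needed per arm for 80% power (normal approximation):

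n = 2 × [0.8 × (1.645 + 0.842) / 0.4]² = 49.5, so 50 per arm (100 completers).

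Power by noncentral t (normal approximation in brackets):
- 28 per arm: 58.0% (58.9%)
- 35 per arm, no attrition: 66.5% (67.2%)
- 35 in total: 42.2% (43.4%)

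The stated 80% is not reproduced. That is a separate matter; the starting point here is 58.0%.

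**Step 2: effect of the covariate.** Let r be the partial correlation of baseline pain with week-6 VuAS given laceration degree. It must be partial, because laceration degree is already in the model and carries part of the variation in initial trauma. Then:
- residual SD = 0.8 × √(1 − r²)
- noncentrality = 0.4 / [residual SD × √(2/28)]
- residual df = 56 − 4 = 52 (intercept, treatment, laceration degree, pain)
- equivalent completers per arm = 28 / (1 − r²)

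The documents give no r, so the values below are assumptions.

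| r | 1 − r² | Residual SD | Equivalent n per arm | Power |
|---|---|---|---|---|
| 0 | 1.00 | 0.800 | 28.0 | 58.0% |
| 0.2 | 0.96 | 0.784 | 29.2 | 59.5% |
| 0.3 | 0.91 | 0.763 | 30.8 | about 61.5% |
| 0.5 | 0.75 | 0.693 | 37.3 | 68.7% |

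The gains are about 1.5, 3.5 and 10.7 points.

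**Step 3: the cost if r is near 0.** One lost degree of freedom (53 to 52) moves power from 58.00% to 57.99%, under 0.1 point. That counts degrees of freedom only. Chance imbalance of the covariate between arms inflates the variance of the treatment estimate by a factor of about 52/51 = 1.02 on average. The noncentrality at r = 0 then falls from 1.871 to 1.871/√1.02 = 1.853, and power to about 57.3%, a loss of about 0.7 point. The same allowance lowers the other rows to about 58.8%, 60.7% and 68.0%. Break-even is where 1 − r² = 51/52, which is r of about 0.14.

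**Step 4: can this restore 80%?** Setting 28/(1 − r²) = 49.5 gives r = √(1 − 28/49.5) ≈ 0.66. Nothing in the documents suggests a correlation that high.

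**The case against.** The best defence is that nothing in the Analysis plan is wrong. Regression adjusted for the stratification factor is a valid analysis of a randomised comparison. VuAS asks about the past four weeks, so a value taken 1–2 days after delivery would describe late pregnancy; its absence is understandable. All of this stands. A reader might infer that the missing baseline biases the treatment comparison. It does not, because randomisation protects the comparison with or without a baseline.

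The prognostic value of the proposed covariate is also unproven. Pain 1–2 days after a laceration is acute wound pain. A reader might take the Significance section as showing that early pain predicts the trial outcome. The study cited there links pain at 1 month to dyspareunia at 6 months (2.45 times; 95% CI 1.93–3.10), so both predictor and outcome differ. Even taken at face value it points to a small gain. Reading 2.45 as an odds ratio and 32.5% as the prevalence of pain (both assumptions), d = ln(2.45) × √3/π = 0.49. Then r = 0.49/√(0.49² + 1/(0.325 × 0.675)) ≈ 0.22, which gives about 60% power. That study is indirect support only, and r = 0.5 has no support in the documents.

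Other covariates could be argued for. The same section gives breastfeeding a larger association with dyspareunia (2.89 times), and plan for breastfeeding is collected. This stands as a reason to consider that variable too. It is not a reason to pre-specify no symptom covariate.

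Last, the imbalance clause could admit baseline pain. It could, but only after the data are seen and in a further analysis, so it neither fixes the model nor secures the precision.

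**Conclusion.** The point holds as a low-cost improvement in precision. The primary week-6 model has no baseline VuAS and pre-specifies no pre-treatment symptom covariate; laceration degree is its only adjustment. On the plan's inputs with 28 completers per arm, a fixed baseline pain covariate would raise power from about 58% by 1.5 to 3.5 points at r = 0.2 to 0.3, and to 68.7% at an optimistic r = 0.5. Allowing for chance imbalance takes about 0.7 point off each figure.

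This rests on an assumed partial correlation that the documents do not give, and on the text being right that the pain score is collected at baseline. A reader might infer that the change rescues the sample size calculation. It does not: r of about 0.66 would be needed, and the gap between the stated 80% and its inputs has to be settled separately. So does the conflict over the primary time point, since the Randomization section gives 12 weeks while Specific Aim 1, the Analysis plan and section F give 6.

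**What to change.** In the Analysis plan:
- Pre-specify the baseline 0–100 perineal pain score as a fixed covariate, alongside laceration degree, in the primary week-6 VuAS regression and the later VuAS models, whatever imbalance is observed.
- State that the score is completed before the REDCap allocation is run. The day of randomisation alone does not guarantee this order.
- Impute a missing baseline score by the overall mean, ignoring arm, so that no woman is dropped for lack of a covariate.

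Elsewhere:
- Reconcile the visit table with the Aim 2 text on baseline questionnaires, and give the perineal pain scale its own row.
- Use different abbreviations for the pain scale and the Vaginal Assessment Scale.

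The cost is a few sentences, one degree of freedom and, if the covariate proves uninformative, under one point of power. No new data are needed if the Aim 2 text is followed. If the score is not in fact planned at baseline, it would have to be added to the enrolment visit.

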Study limitations include retention difficulties and compliance issues. Dropout will be minimized by telephone or text reminders one week prior to patients' scheduled postpartum visit and attempts will be made to schedule study visits on same day of routine obstetrical postpartum visits for the first follow up visit. Eligible patients will also include only patients with a history regular prenatal care by an obstetrician with offices affiliated with the Wexner Medical Center. If participants are unable to attend their scheduled visit, a phone interview will be conducted to fill out questionnaires. In addition, patient adherence to twice weekly application in vaginal estrogen and placebo groups will be noted. Again text reminders will be used to encourage compliance. Patients will be asked about adherence at each follow up visits and reasons for discontinuation or deviation from instructions will be noted.

Specific Aim 2: To estimate the effect of local vaginal estrogen in the postpartum period on perineal pain, quality of life, and sexual function.

Background, preliminary results and rationale

In order to effectively evaluate the impact of each group on perineal pain, quality of life, and sexual function in the early postpartum period, we will administer baseline and follow-up questionnaires. Changes will be assessed using validated questionnaires consisting of a visual analog scale for pain (VAS) and Edinburgh Postnatal Depression Scale (EPDS). Researchers in the field of Female Pelvic Medicine and Reconstructive Surgery have also created several validated questionnaires to assess these measures. We will be able to objectively assess quality of life by using the following validated questionnaires: The Urinary Distress Inventory (UDI-6), the Fecal Incontinence Severity Index for bowel symptoms (FISI), and the Female Sexual Function Index (FSFI). These questionnaires have consistently been used in landmarks trials in the assessment of female pelvic floor disorders.

Research Design

1. Perineal pain: The VAS scale ranges from 0 to 100 with 100 indicating maximum pain.

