2. *Quality of Life measures*: The **EPDS** is a validated 10-question depression assessment for postpartum women, which includes anxiety symptoms and excludes constitutional symptoms associated with depression common in the postpartum period, such as changes in sleeping patterns. Each question is given a score of 0 to 3 and a total score of at least 10 indicates minor or major depression at the time of the patient's follow-up; The **UDI-6** is a questionnaire that includes 6 items evaluating bother form urinary symptoms with higher scores indicating more bothersome symptoms; The **FISI** evaluates patient responses symptom severity to fecal incontinence with higher scores indicating more bothersome anal incontinence symptoms.

3. Sexual function: The **FSFI** is a validated questionnaire to assess sexual function in six domains of sexual function, including desire, arousal, lubrication, orgasm, satisfaction, and pain over the 4 weeks prior to administration of questionnaire with lower scores indicating more sexual dysfunction.

Questionnaires will be administered to all groups at baseline enrollment and clinic encounters at 6 weeks and 12 weeks. See Fig 1.

Statistical Analysis

Similar to analyses proposed in Aim 1, secondary endpoints will be analyzed via generalized linear mixed models or linear generalized estimating equation models (GEE), adjusting for stratification factors and accounting for correlation over time.

Anticipated results

Assuming an improvement in perineal symptoms associated with vulvar atrophy with local estrogen use, patients will have a significant improvement in perineal pain, quality of life, and sexual function.

Pitfalls and Solutions

Again retention and compliance is a concern in the postpartum period. Strategies including telephone and text reminders will be utilized. If patients are unable to attend their follow-up visit, a study member will call the patient and record the patient's responses.

Specific Aim 3: To compare patient satisfaction, ease of product use, likelihood of continued use, and rates of adverse events for the vaginal estrogen and placebo groups.

Background, preliminary results and rationale

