We do not anticipate an impact on lactation supply or practices given the lack of sustained increased serum estradiol levels in prior studies. Furthermore, in a systematic review of estrogen-containing contraceptives among breastfeeding women, the authors note an inconsistent impact of estrogen-containing contraceptives on breastfeeding when initiated prior to 6 weeks postpartum. In fact, the authors highlight a fair quality study demonstrating no impact on supplementation or breastfeeding continuation of estrogen-containing contraceptives when compared to progesterone-only pills.²⁰

This study will only include female participants who are at least 18 years old. We will not limit the study based on race, unless unable to provide consent in English, as all patients who will undergo a vaginal delivery with subsequent perineal laceration at Wexner Medical Center will be taken into consideration for eligibility

IRB Approval

This study is currently approved by the Ohio State University Wexner Medical Center IRB.

F. EVALUATION CRITERIA AND PROGRESS

Study Visits

The participants will be randomly assigned to estrogen cream or placebo for 12. The primary outcome is difference in tissue quality via the VuAS at 6 weeks between patients randomly assigned to vaginal estrogen versus placebo cream. Secondary outcomes will compare the effect of local estrogen on: VuAS at 6 and 12 weeks, the VAS at 6 weeks and 12 weeks, perineal pain, quality of life, and sexual function as measured by validated questionnaires in the field of Female Pelvic Medicine and Reconstructive Surgery at 6 weeks and 12 weeks. Patient satisfaction and treatment continuation will be measured at each follow up visit. (Table 2: Study Assessment by Visit).

G.POINT OF CONTACT

[name] Clinical Fellow, Female Pelvic Medicine and Reconstructive Surgery Department of Obstetrics and Gynecology The Ohio State University [name] [contact] [contact] Email: [contact]

Aims	Evaluation	Baseline	Week 6	Week 12			
	Consent	Х					
	Demographics	Х					
Aim 1	Pelvic Exam		Х	Х			

	VuAS	х	х
	VAS	Х	Х
	VaginalpH	Х	х
	MI	Х	х
Aim 2	EPDS	Х	Х
	UDI-6	Х	Х
	FISI	Х	х
	FSFI	Х	Х
Aim 3	Patient satisfaction	Х	Х
	Continued use	Х	Х

STUDY TIMELINE

Month		2	3	4	5	6	7	8	9	10	11	12	13	14
IRB approval														
Recruitment														
Data Collection														
Data analysis														
Preparation of results														
Study Closeout														

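### Aim 2 baseline questionnaire scores are collected, but the Aim 2 model does not say how they are used; making each one a fixed covariate would be a nearly free gain in precision

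*Combined protocol and SAP*

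**What the plan says.** **Collection.** Three places require baseline scores. Specific Aim 2, in the Specific Aims, lists the five instruments and says "These questionnaires will be completed on day of randomization and" at the 6- and 12-week visits. The Aim 2 background says "we will administer baseline and follow-up questionnaires". The Aim 2 Research Design says "Questionnaires will be administered to all groups at baseline enrollment and clinic encounters at 6 weeks and 12 weeks".

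**Model.** The Aim 2 Statistical Analysis section analyses the endpoints "via generalized linear mixed models or linear generalized estimating equation models (GEE), adjusting for stratification factors and accounting for correlation over time". The only stratification factor, defined under Randomization, is laceration degree (2nd versus 3rd/4th). No baseline score is named.

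**Other text bearing on baseline.**
- The Aim 2 background says "Changes will be assessed using validated questionnaires consisting of a visual analog scale for pain (VAS) and Edinburgh Postnatal Depression Scale (EPDS"), which suggests change from baseline but defines no change endpoint or model term.
- The Aim 1 Analysis plan, to which Aim 2 is said to be similar, says "Any chance imbalance in characteristics known to be related to primary or secondary outcomes will be considered as adjustment variables in outcomes analyses". For the primary outcome it adds "Further analysis will consider adjustment for chance imbalances in key patient characteristics". It gives no list of characteristics, no threshold for imbalance, and no mention of baseline questionnaire scores.
- Section F, Study Visits, places the secondary comparisons on "questionnaires in the field of Female Pelvic Medicine and Reconstructive Surgery at 6 weeks and 12 weeks".

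The assessment table in Section F did not survive text extraction well enough to show which visits its marks belong to, so I do not rely on it.

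**The concern.** Participants complete five questionnaires one or two days after delivery, and the plan then does not say what those scores are for. The text allows four uses:

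1. not used at all;
2. one of three repeated responses in the longitudinal model;
3. the base of a change score;
4. a covariate, considered only if the arms happen to differ at baseline.

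These do not give the same precision. Aim 2 is framed as estimating an effect, and the pilot will have few completers, so precision is what matters most here. A covariate improves precision by explaining outcome variance, and it does so even when the arms are balanced. A rule that adjusts only after an imbalance is seen therefore gives up most or part of the benefit, depending on a threshold that the plan does not state. Leaving the choice open for five instruments also leaves five analytic decisions to be made after the data are seen.

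**Working it through.** **No Aim 2 figure to reproduce.** The plan makes no power or precision statement for Aim 2. The sample-size section concerns the VuAS only. Whether its 80% figure is right is a separate question and does not affect this one.

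**Inputs**
- From the documents: 70 randomised 1:1 and 20% attrition at week 6. 70 × 0.8 = 56, or 28 per arm. (The same section states that 35 patients will complete; I use the arithmetic.) Two-sided 10% is borrowed from the primary endpoint.
- Assumed: a 0.5 SD effect at one visit, and baseline to follow-up correlation ρ of 0.2, 0.3, 0.5 or 0.7. The documents give neither.

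**Formula.** The standard error of the treatment difference, in follow-up SD units, is √(V × 2/28), where V is the variance factor:
- baseline ignored: V = 1
- baseline as covariate: V = 1 − ρ²
- change score: V = 1 + k² − 2ρk, with k the baseline SD over the follow-up SD; at k = 1 this is 2(1 − ρ)

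Power comes from the noncentral t, with the laceration stratum in the model (53 df, or 52 with the covariate).

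With baseline ignored, SE = √(2/28) = 0.267, noncentrality = 0.5/0.267 = 1.87, and power = 58.0%.

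| ρ | V, covariate | Power, covariate | Equivalent n per arm, 28/V | V, change (k = 1) | Power, change |
|---|---|---|---|---|---|
| 0.2 | 0.96 | 59% | 29.2 | 1.6 | 43% |
| 0.3 | 0.91 | 61% | 30.8 | 1.4 | 47% |
| 0.5 | 0.75 | 69% | 37.3 | 1.0 | 58% |
| 0.7 | 0.51 | 83% | 54.9 | 0.6 | 77% |

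The 90% confidence interval half-width is 0.447 SD ignoring baseline, and 0.439, 0.427, 0.388 and 0.320 SD with the covariate.

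A change score is worse than ignoring baseline whenever ρ < k/2. At ρ = 0.5 its power is 69%, 58% or 40% for k = 0.5, 1 or 1.5.

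**Repeated response.** If the arm means are left free at baseline, the visit-specific contrast behaves like the unadjusted comparison, and the treatment-by-time contrast against baseline behaves like the change score. If the arm means are constrained equal at baseline, precision is essentially that of the covariate. The plan does not say which.

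**Adjusting only after an imbalance.** Simulated with normal scores, one visit, no stratum and 100,000 trials per cell. Fixed adjustment comes out slightly below the formula because the formula ignores the cost of chance baseline differences.

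| Rule | Power, ρ = 0.5 | Power, ρ = 0.7 |
|---|---|---|
| never adjust | about 58% | about 58% |
| adjust if baseline p < 0.05 | 58% | 59% |
| adjust if baseline p < 0.10 | 59% | 61% |
| adjust if standardised difference > 0.25 | 62% | 67% |
| adjust if standardised difference > 0.1 | 65% | 76% |
| always adjust | 68% | 82% |

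**Type I error at nominal 10%** (40,000 null trials per ρ). Adjusting only if baseline p < 0.10 gives 9.8%, 9.7%, 8.7% and 7.1% at ρ = 0.2, 0.3, 0.5 and 0.7, which is conservative. Reporting whichever of the adjusted and unadjusted p-values is smaller gives about 12%, 13%, 14% and 16%.

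**The case against.** The best reply is that the plan does imply a use for baseline. The Aim 2 schedule lists three time points, the analysis section that follows accounts for correlation over time, and the background speaks of changes. A repeated-measures model with baseline as one of three responses is a natural reading, and with arm means constrained equal at baseline it would already have almost all the precision sought here. This has force. A reader might infer that baseline scores enter only through the chance-imbalance rule, and the documents do not support that. What remains is that the plan never chooses among the readings, and the table shows that they differ materially.

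A reader might also infer that the plan inflates the false-positive rate. It does not. A rule that adjusts when imbalance is seen is conservative in the simulation above (about 7% to 10%). The 12% to 16% figure needs an analyst who freely reports the better of two results, and no section proposes that. The plan limits adjustment to characteristics known to relate to outcome and, for the primary outcome, places it in further analysis.

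The size of the gain also rests on an unstated correlation. Baseline is taken 1-2 days after delivery with a fresh laceration, so early scores may predict week 6 poorly. For the FSFI the 4-week recall would fall mostly before delivery. At ρ of 0.2 to 0.3 the covariate adds only about 1.5 to 3.5 percentage points of power. This limits the severity. It is not a reason to leave the role open, because at those same correlations a change score with equal SDs costs 11 to 15 points.

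**Conclusion.** The point holds as a free improvement of modest severity. The Aim 2 baseline scores are required, and their role in the analysis is not settled. The randomised comparison is unbiased on average under every reading; the issue is precision and prespecification, not validity.

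Prespecified covariate adjustment cuts variance by 4%, 9%, 25% or 49% at ρ = 0.2, 0.3, 0.5 or 0.7. These proportions depend only on ρ, not on the assumed effect, alpha or sample size. The power figures do depend on the assumed 0.5 SD effect, the borrowed two-sided 10% and 28 per arm, and a single follow-up visit; two correlated visits would change the figures but not the direction. The gain is material at ρ of 0.5 or more and small at 0.2 to 0.3, and the documents do not show which applies. Because these are secondary endpoints in a pilot, nothing here threatens the trial's main purpose.

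**What to change.** Add to the Aim 2 Statistical Analysis section:

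> Each questionnaire score at weeks 6 and 12 will be modelled with treatment, visit, treatment-by-visit interaction, laceration stratum and the participant's own baseline score as a prespecified covariate, whether or not the arms are balanced at baseline. Treatment contrasts will be reported at week 6 and at week 12.

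An equivalent alternative is to keep baseline as a response at three time points, with arm means constrained equal at baseline, and report the same two contrasts. This version keeps participants whose baseline score is missing. If the covariate version is chosen, add how a missing baseline score will be handled.

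The cost is a sentence or two and about one degree of freedom per outcome. The baseline data are already required, so there is no extra visit, questionnaire or recruitment.
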